## **Background and Study Rationale**

### **IV Access for In-hospital Patients**

In-hospital patients are commonly subjected to repeated intravenous infusions and medication administrations. The repeated placement of intravenous catheters is thought to compromise the integrity of superficial veins. Hence, finding a suitable peripheral vein continues to be a recurring challenge for healthcare providers. In addition, complications associated with venous access placement are a common burden, including hematomas, phlebitis, thrombophlebitis, infiltration, and nerve damage. Therefore a tremendous need for easier and more reliable intravenous access is present.

### **Near-infrared Superficial Vein Imaging**

Recently, vein imaging devices became available in the form of portable devices utilizing near-infrared (NIR) light at a wavelength of approximately 850 nm to create a real-time map of superficial veins. With these devices, NIR light is projected onto the surface of the patient's skin where it can penetrate depending on the device's light intensity typically up to 10 mm deep into the tissue [1]. Once NIR propagates through the tissue it encounters some degree of absorption dependent on the characteristics of the tissue molecules. With hemoglobin having a much greater absorption coefficient compared to most other tissue molecules [2], the reflected light signal provides a negative contrast image of blood vessels. While the depth of visualization of blood vessels is dependent on specific tissue conditions, larger vessels underneath the skin typically used for peripheral venous access are expected to be visualized reliably using this technology.

[figure not shown]

Figure 1: VeinViewer Flex (Christie Medical Holdings, Inc., Memphis, TN)

With the expected improvement of visualizing superficial veins, the manufacturers of these devices proposed anticipated clinical benefits to include increased identification of suitable venous access sites, better choice of catheter gauge, and better identification of potential problem locations within veins such as valves and bifurcations. In select circumstances, flushing of the placed IV catheter under NIR visualization may also

provide improved information about the patency of the vein. Overall, improvement in peripheral venous access using this technology may theoretically avoid more invasive venous access catheters, such as peripherally inserted central catheters or central venous catheters.

In the clinical setting, NIR technology has shown to significantly increase the number of identifiable possible cannulation sites compared with normal eyesight [3,4]. However, the improvement in visualization did not automatically translate into improvement in successful cannulation of veins. Specifically, the efficacy of these vein finding devices has shown limited benefit when tested in the pediatric in-hospital population with a nonselective use in all patients. A meta-analysis of 11 RCTs concluded that using NIR light devices did not have an impact on overall failure rate at the first attempt at peripheral intravenous cannulation (PIVC) in pediatric patients [5]. Similarly, in studies evaluating the number of attempts required for successful PIVC found no difference between the NIR light device and traditional methods [6]. Many investigators subjectively felt the NIR device to be helpful; particularly in selected patients [5]. Yet, subgroup analysis did not define the cohort of pediatric patients that would benefit most from this technology. One publication interpreted these outcomes as such that despite improved visualization of superficial veins, successful venous puncture remains heavily dependent on the skills of the operator [7].

The efficacy of NIR vein finders beyond the first line approach, particularly in patients that have failed conventional peripheral venous access methods or in patients that are expected to be a “difficult stick”, is not established. Conflicting results have been reported in the pediatric literature regarding the subjective benefit of NIR light devices in patients with perceived difficult peripheral intravenous access [6]. In addition, knowledge about the efficacy of these devices in the adult inpatient setting is mostly unknown. The aim of the present study is to address these knowledge gaps.

## **Study Objectives**

The objective of this project is to define the effectiveness and therefore the role of NIR vein finders in adult patients with difficult peripheral venous access. The specific objective of the proposed randomized controlled trial is to test the clinical success rate of placing peripheral venous catheters in 'difficult' access patients using traditional peripheral venous catheter placement compared to two established methods utilizing NIR vein imaging. We hypothesize that the capability to successfully place lasting peripheral venous catheters is increased with the adjunct of the imaging technology, reducing the number of failed needle sticks, reducing the number of peripheral venous catheters placed throughout a patient's hospital stay, and reducing the need for more invasive catheters such as PICC lines. To test this hypothesis, we utilize a commercially available FDA-approved NIR vein finder which currently is already in clinical use at Lahey Hospital & Medical Center. We are planning to conduct a randomized controlled trial recruiting patients who as part of their routine clinical care will require placement of a peripheral venous catheter and who are considered to have a difficult peripheral venous access. Potential study patients will be randomized into 3 groups:

- Placement of peripheral venous catheter using conventional methods
- Use of a VeinViewer to visualize the most suitable target. Once the target has been identified and marked, the device will be placed aside and the peripheral venous catheter will be placed using conventional methods
- Identification of the most suitable target and placement of a peripheral venous catheter under constant imaging with a VeinViewer

To achieve the goals of this project, we have assembled a highly interdisciplinary team with expertise in clinical peripheral venous catheter placement, biomedical device development, and biostatistics to pursue the following specific aims:

### **Primary Objective**

- to assess the rate of successful initial placement of a peripheral venous catheter dependent on the method used

### **Secondary Objectives**

- to compare variables representing the ease of peripheral venous catheter placement, complication rates, and durability of the catheter within each study treatment arm

## **Study Design**

### **Study Overview**

The proposed project is a randomized controlled trial involving in-hospital patients who receive routine care at Lahey Hospital & Medical Center, Burlington, MA and as part of their planned treatment are scheduled to undergo placement of a peripheral venous catheter in one of the upper extremities. 400 patients (age  $\geq 18$ ), who are scheduled and consented to undergo placement of a peripheral venous catheter in one of the upper extremities as part of routine clinical care and who meet the criteria listed below, will be enrolled. Patient recruitment is expected to take 8 months. Patients will be randomized to 1) placement of a peripheral venous catheter using conventional methods *versus* 2) use of NIR vein imaging to visualize the most suitable target and subsequent placement of a peripheral venous catheter using conventional methods *versus* 3) placement of a peripheral venous catheter under constant imaging with NIR vein imaging. Clinical outcomes obtained will be recorded and analyzed.

### **Eligibility Criteria**

The eligibility criteria were chosen to minimize the risk to the study patient by only including patients who are already planned to undergo placement of a peripheral venous catheter and by excluding any high-risk patients. In order to be considered for the study, patients have to meet the following criteria:

a) Inclusion criteria:

- adult in-hospital patients ( $\geq 18$  years of age, inpatient and outpatient setting)
- willing to provide research authorization
- scheduled and consented to undergo peripheral venous cannulation of one of the upper extremities to be performed by one of the members of the Vascular Access Team
- determined to be a difficult peripheral venous access defined by one of the following criteria in alignment to the A-DIVA scale to be assessed by one of the members of the Vascular Access Team [8]:
  - failed inspection for more than one visible or palpable suitable vein through conventional methods
  - failed at least one attempt of peripheral venous cannulation through any methods
  - history of difficult peripheral venous access
  - greatest diameter of target vein less than 3mm determined by conventional methods

b) Exclusion criteria:

- clinical contraindication for placement of peripheral venous catheter, including:
  - severe bilateral upper extremity edema
  - severe bilateral upper extremity skin burn
  - severe bilateral upper extremity cellulitis
  - history of bilateral axillary lymphadenectomy

- known severe cardiovascular or pulmonary compromise demanding minimization of procedure time, such as:
  - severe shock with severe cardiovascular instability
  - active CPR
  - major uncontrolled hemorrhage
  - any condition for which the primary healthcare provider is requesting emergent venous access
- scheduled PICC or midline catheter placement
- non-English-speaking patients if an interpreter is not available
- prisoner and any individual involuntarily confined or detained in a penal institution
- impaired capacity to make informed medical decisions

### **Recruitment**

In-hospital patients seen at Lahey Hospital & Medical Center who meet study criteria will be identified by a member of the hospital's Vascular Access Team through direct referral by the patient's clinical care provider. Patients will be approached by the team member at the time of planned placement of a peripheral venous catheter. For patients who are interested in participating in the study and who meet criteria, a verbal informed consent will be obtained in person by the team member. In addition, a written brochure explaining the study will be provided. An application for waiver of written consent will be submitted to the institution's IRB. Recruitment will continue until 400 patients who meet eligibility criteria have been enrolled. It is expected that patient recruitment for the study will be completed within 8 months.

### **Informed Consent Process**

A written informed consent will be obtained in person from eligible patients by a member of the hospital's Vascular Access Team at the time of planned placement of a peripheral venous catheter. The team members have been trained regarding the required elements of information needed to be provided to the patient. In addition, the patient will also receive the information in writing through a brochure provided to the patient at the time of consent. An additional, unsigned copy of the consent form will be given to the patient at the time of consent. The consent form itself will be collected and scanned into the patient's electronic medical records at a later point. A copy of the consent form will be archived in the study folder at a later point.

The person obtaining consent from the study patient will give subjects detailed and comprehensive information about the study, its associated risks, benefits, expected outcomes, and alternative options. For non-English-speaking patients, an interpreter will translate the provided consent information to the potential subject and interpret any questions for the Vascular Access Team member.

Study patients may withdraw at any time by informing the Vascular Access Team member or the principal investigator verbally or in writing. Yet, data already collected and/or generated prior to withdrawal will not be affected.

## **Study Procedures**

### **Imaging System To Be Utilized**

For the study purposes the commercially available FDA-approved VeinViewer Flex (Christie Medical Holdings, Inc., Memphis, Tennessee) will be utilized. The device provides HD imaging and projection of NIR images at a minimum brightness of 5 lumens. The device weighs 0.7 kg and measures 11.6" x 4" x 1.7". It is powered by standard lithium ion batteries or AC outlet. The imaging focal distance is 30 cm. The VeinViewer Flex uses no consumables, requires no patient contact, and does not provide any heat, laser-safety, eye-safety, or radiation concerns. It is considered on FDA class I device and received 510(k) exempt approval for the intended use to indicate the location of blood vessels.

Figure 2: VeinViewer Flex (Christie Medical Holdings, Inc., Memphis, TN)

The device includes distinctive visualization modes through the provided VeinViewer ASSESS Imaging Suite. These include:

- Universal: provides the brightest and most accurate direct-projection, baseline mode  
Purpose: minimizing surface structures such as hair and wrinkles
- Fine Detail: enhances finer structures  
Purpose: identifying small veins in pediatric patients
- Inverse: switches/inverts colors within the image window  
Purpose: customizing the projected image based on factors such as skin tone, density of hair follicles, and room brightness
- Resize: choice of one of three window sizes  
Purpose: for pediatric patients or when focus on only one vessel is needed
- MaxBright: increases image brightness by an additional 40%  
Purpose: for scenarios where greater than standard ambient lighting is present

It is left to the discretion of the Vascular Access Team member to decide which mode is being used during the study procedure. Yet, historically it is expected that most of the time the 'Universal' mode will be utilized.

[figure not shown]

Figure 3: Visualization modes of the VeinViewer ASSESS Imaging Suite

### Training of Staff

Each member of the Vascular Access Team involved in a study underwent formal training in the proper use of the VeinViewer device provided by the device manufacturer or hospital. In addition, each member had to use the device independently during routine patient care for at least 20 times before being able to participate in the study. Research training in the form of successful completion of the institutionally required CITI program is mandatory for each participating team member. Additional training on the consent process was provided.

### Peripheral Venous Cannulation and Randomization of Study Groups

Patients, who meet eligibility criteria and agree to participate in the study after an informed consent process, will undergo simple randomization. A sealed envelope holding the information of the random assignment will be opened by the Vascular Access Team member. Randomization will assign study patients into 1 of 3 groups/treatment arms with a 1:1:1 ratio:

- Placement of a peripheral venous catheter using conventional methods
- Use of VeinViewer to visualize the most suitable target. Once the target has been identified and marked, the device will be placed aside and the peripheral venous catheter will be placed using conventional methods
- Identification of the most suitable target and placement of a peripheral venous catheter under constant imaging with VeinViewer

When the VeinViewer device will be utilized, multiple areas on the patient's upper extremities will be assessed looking for the most suitable access point according to routine clinical practice. There is no restriction in regards to vein diameter, vein length, or relation of veins to joints. The choice of the location for intravenous cannulation, the use of tourniquets, the use of heating devices, and any techniques to palpate the vein will be left to the discretion of the Vascular Access Team member based on routine clinical practice. This study requires an unobstructed view of the subject's arm under standard hospital lighting conditions.

Investigators have up to 30 minutes or ONE attempt before the study allows for change of technique to the preference of the Vascular Access Team member.

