### **Sample Size and Power Determination**

The study was designed such that we will need to enroll at least 125 patients per group (375 patients total for all three groups) to have 80% power if the estimated percentage with success in the control group is 50% and 70% in either of the study groups using a two-sided  $p < 0.0167$  for determining significance (study alpha was divide equally between the three groups).

We have therefore chosen to include 400 patients in the study. We anticipate that this initial data set will provide useful information regarding the effectiveness of the device in difficult access situations. In addition, it will give information about variability of data between patients that will guide the design of any future device and further studies that will answer more specific clinical questions.

Due to the need for appropriately trained staff to be available, the study will only be offered during hours when one of the trained Vascular Access Team members / co-investigators is available. During this time frame, the Vascular Access Team typically encounters approximately 50 patients per week. We anticipate that approximately 40% of these patients will meet study inclusion criteria. We estimate an approximate 60% study recruitment rate. We therefore expect that approximately 12 patients will be recruited into the study per week. The study is therefore estimated to be complete within 8 months.

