## **Limitations**

Overall it is felt that the study has a very robust design. Yet, limitations include bias by any Vascular Access Team member who may favor one method and therefore might create more favorable results with the method of subjective preference (observer-expectancy effect and experimenter bias).

The follow-up was felt to be adequate since most complications are expected to present during the hospital stay. However, long-term complications, such as thrombophlebitis, might be slightly underestimated due to its sometimes later presentation even after removal of the catheter or in patients who have been transferred to a different facility with the catheter still in place. Nevertheless, there is currently no reason to believe that long-term outcomes of a successful peripheral venous catheter are dependent on the method of catheter placement and therefore it is not expected that the study results will significantly be affected.

NIR vein imaging might require a learning curve. To minimize the issue, all Vascular Access Team members have been trained with the device and had to use the device independently during routine patient care for at least 20 cases before being able to participate in the study.

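### Allocation rests on a sealed envelope opened by the operator, with no numbering, link to a patient before opening, or reconciliation described

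*Combined protocol and SAP*

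**What the plan says.** The section Peripheral Venous Cannulation and Randomization of Study Groups says that patients who are eligible and have consented undergo simple randomization in a 1:1:1 ratio. It then says: "A sealed envelope holding the information of the random assignment will be opened by the Vascular Access Team member". Nothing more is said about concealment. Opacity, sequence numbers, who prepares or holds the envelopes, a log, and any marking before opening are not mentioned. Data Collection gives each patient a study number but does not tie it to an envelope.

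The neighbouring steps belong to the same role. Under Eligibility Criteria, a Vascular Access Team member decides whether access is difficult. Any one of four criteria is enough, and some rest on judgement, such as failed inspection for a suitable vein or a history of difficult access. Under Recruitment, "Patients will be approached by the team member at the time of planned placement of a peripheral venous catheter". Team members also obtain consent and place the catheter.

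Limitations states that "limitations include bias by any Vascular Access Team member who may favor one method and therefore might create more favorable results" and classes this as observer expectancy and experimenter bias. Study Monitoring sets a review every four weeks of consent, eligibility compliance, protocol violations and data integrity. Envelopes and allocation order are not on that list.

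**The concern.** The operator has to know the arm in order to do the procedure, and no independent assessor of the primary outcome is named. Concealing the assignment until the patient is committed is therefore one of the few protections against bias that this design can have. The person most likely to hold a preference is also, in role, the person who handles the envelope. If an envelope were opened early, exchanged or discarded, easier patients could drift towards one arm.

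Later analysis could do little about this. The listed data do not include which difficulty criterion a patient met. Apart from the patient's report of the usual number of attempts, the ratings of difficulty come mainly from the unblinded operator. Concealment also cannot be restored once patients have been randomised.

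**Working it through.** **1. The plan's own figure, to show what the point does not touch.** Sample Size and Power Determination gives "80% power if the estimated percentage with success in the control group is 50% and 70% in either of the study groups", "using a two-sided" threshold of 0.0167 ("study alpha was divide equally between the three groups", that is 0.05/3), and 125 patients per group. With pooled variance and no continuity correction:

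n = [z(1−α/2)·√(2·p̄·(1−p̄)) + z(0.80)·√(p₁(1−p₁) + p₂(1−p₂))]² / (p₁−p₂)²

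with p̄ = 0.60:

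n = [2.393 × √0.48 + 0.842 × √0.46]² / 0.20² ≈ 124.2, rounded up to **125**.

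The stated number reproduces. Power is 80.3% at 125 per arm and 83.0% at 133 (400/3). Better concealment changes none of this.

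**2. Routes by which allocation could be influenced, set against the text.**

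| Route | What stands in the way | Described check that would reveal it |
|---|---|---|
| Predicting the next assignment from earlier ones | Simple randomization; route closed | Not needed |
| Opening early, or reading through the envelope | Stated order: eligibility and consent first | None |
| Taking a different envelope | Only one envelope is provided for each patient | None: no number, no link to the patient |
| Dropping the patient after opening | Eligibility is settled before opening | At most, a consent form with no trial data to match |

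The last check depends on the Informed Consent Process section, where written consent is obtained, scanned and archived. The Recruitment section instead describes verbal consent with a waiver of the written form. In neither case is anyone told to match forms to envelopes.

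Arm sizes would not give the problem away. An exchange leaves the counts unchanged. Under simple randomization the count in one arm of a 400-patient trial has standard deviation √(400 × 1/3 × 2/3) ≈ 9.4, so a few discarded envelopes would be lost in ordinary variation. Recruitment runs until 400 eligible patients are enrolled, so a dropped patient is replaced.

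**3. How much steering would matter (illustration).** From the plan: 133 per arm and two-sided 0.0167. Assumed, not in the documents: no true effect; half the patients easier (70% success) and half harder (30%); a net fraction s of each of two arms exchanged, all in one direction. The share of easier patients becomes 0.5 + s in one arm and 0.5 − s in the other, so

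spurious difference d = 2·s·(0.70 − 0.30).

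For s = 5% (0.05 × 133 ≈ 7 patients per arm), the arms have 52% and 48% success and d = 0.04. The null standard error is √(2 × 0.25/133) = 0.0613. The rejection probability is about Φ(0.04/0.0613 − 2.393) + Φ(−0.04/0.0613 − 2.393) = Φ(−1.74) + Φ(−3.05) ≈ 0.042.

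| Net exchange s per arm | Spurious difference | False positives, one comparison |
|---|---|---|
| 0 | 0 points | 1.7% |
| 2.5% | 2 points | 2.3% |
| 5% | 4 points | 4.2% |
| 10% | 8 points | 13.8% |
| 15% | 12 points | 33.0% |

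If preferences differ between operators, s is the net figure and falls towards zero as they cancel. The route of dropping patients after opening is not modelled.

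**The case against.** The plan is better than a bare reading suggests. It fixes the order of eligibility, consent and then opening, and it speaks of a single envelope. Taking another one, or reversing eligibility afterwards, would be misconduct and not something the plan allows. Simple randomization removes the usual guessing route. The four-weekly review looks at eligibility, consent and violations, and archived consent forms could expose a dropped patient. All of this stands. What remains is that nothing described would show an exchanged or prematurely opened envelope.

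A reader might infer several stronger things that the documents do not support:

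- **That steering would leave no trace.** An unmatched consent form might remain for a patient dropped after opening. The defensible statement is that no described check would reveal an exchange.
- **That one person does everything alone, several operators recruit in parallel, and the operator scores success.** Steps are assigned by role. One person doing them all is the natural reading, since the study is offered whenever one trained member is available, but it is not stated. Parallel recruitment is not stated either, and no outcome assessor is named.
- **That the protocol itself names allocation steering as its main weakness.** Limitations lists operator preference among its limitations and describes bias in performing and observing. Perfect concealment would not remove that bias.
- **That steering is expected or happened.** Nothing indicates this, or a shared direction of preference.

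The magnitude is also fairly challenged. It rests entirely on assumed one-directional exchange and a clean 70%/30% sort.

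**Conclusion.** The point holds as a gap in the allocation procedure. A role with an acknowledged possible preference handles unmarked envelopes, and neither the randomization section nor the monitoring section provides a way to verify that each envelope went to the patient it was meant for. Under the stated assumptions, a net exchange of 5% per arm is worth 4 points and takes one comparison's false-positive rate from 1.7% to about 4%. The documents give no basis for saying how likely any such exchange is. The sample size is unaffected. This is an inexpensive improvement that should be made; it does not show that the design is unsound. It leaves the performance and observer bias named in Limitations where it was.

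**What to change.** In Peripheral Venous Cannulation and Randomization of Study Groups, state that:

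- envelopes are opaque and numbered in one sequence, or in one numbered run per operator;
- the operator first records eligibility and consent, then writes the study number and the time on the next unopened envelope, and only then opens it;
- every opened envelope counts as a randomised patient in the assigned arm, whatever follows. This removes any gain from dropping a patient after opening, and it matters because Data Analysis and Statistical Methods defines no analysis population.

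In Study Monitoring, add reconciliation of envelope numbers against consent forms and enrolled patients at each four-weekly review.

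The cost is numbering the envelopes, one bedside entry per patient, and a few minutes at a meeting that already takes place. No staff are added. The downside is that patients found ineligible after opening stay in the denominator.
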